#### Part 2: Monitor more closely the course of respiratory function over time in patients with ALS by using remote pulmonary function testing, performed via telemedicine.

*Primary Hypothesis:* Home respiratory assessment enables thresholds for Non-invasive ventilation (NIV) recommendation to be met in the experimental group significantly closer to the initiation criteria, at a time when quality of life is higher, compared to the control group.

*Secondary Hypothesis:* Telemonitoring of respiratory health in the experimental group will maintain higher quality of life, and lengthen survival.

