Following the initial visit (month 0), participants will undergo randomization. Those randomized to the experimental group will be shipped an rPFT kit and scheduled for monthly telemedicine appointments between clinic visits. On the dates of the telemedicine appointments, the respiratory therapist administers the study survey and conducts an rPFT from clinic with the patient in their home. This is repeated for the 2nd month. On the 3rd month, the participant dyad is seen by the therapist during their normal clinic visit. This pattern is repeated until the 5th clinical appointment (including the visit at month 0), resulting in 5 in-person assessments and 8 intermediate tele-assessments over the course of approximately 12 months. The control arm will receive standard assessments during regular ALS clinic appointments (Table 1), and be required to complete a study survey each month. Study procedures will be followed until the study endpoint at month 12, even if NIV is initiated during this period. The treating neurologist will make the decision to end the protocol early if the patient is unable to perform the procedures. The patient can also opt to end the study at any time.

The study survey is administered once a month for participants in both study arms and consists of four parts. The initial survey administered at month 0 will be completed with a researcher present. The remaining surveys will be completed online. If it coincides with administration of a PFT or rPFT, it will be administered first. It is designed to measure the impact of daytime breathlessness and sleepiness on QoL and consists of the following components.

- 1) Sleep Apnea Quality of Life Index (SAQLI) - part D [Flemons1998]. It is designed to assess quality of life pertaining to sleep disturbances, as well as the impact of treatment on QoL. It has been used as a sensitive measure of health-related QoL in ALS [Bourke2006, Jackson2001, Bourke2003].
- 2) Motor Neurone Disease Dsypnoea Rating Scale (MDRS) - subscale D [Dorman2007]. Dorman et al. described an ALS-specific assessment, the Motor Neurone Disease Dsypnoea Rating Scale (MDRS), as one with high construct validity and responsiveness. The dyspnea subscale (MDRS-D) of this tool has patients choose which activities of daily living they have experienced shortness of breath in the past two weeks and how severe the episode was [Dougan2000].

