### **8.3 Statistical methods**

Part 1: The primary hypothesis is that there is no difference in the results of PFT and rPFT for respiratory assessment of FVC and MIP. We will use a paired sample t-test to determine if the mean test results are comparable between the standard and experimental treatments. We will conduct a qualitative analysis to determine whether the patient, caregiver, and therapist determine the rPFT to be an effective way to conduct tests of breathing function.

Part 2: The primary outcomes will be analyzed to determine if respiratory parameters are closer to the actionable threshold at NIV recommendation and whether QoL is better sustained at this point in individuals in the experimental group. This will be done using a non-parametric two sample test of means, the Wilcoxon-Mann-Whitney rank sum test.

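### Section 7.2.2 gives two conflicting modes for the Part 2 surveys; if the therapist-administered one is followed, survey mode differs by arm in the primary quality-of-life comparison

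*Combined protocol and SAP*

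**What the plan says.** Three statements in Section 7.2.2 bear on how the monthly survey (SAQLI, MDRS-D, SF-36) is collected.

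- Experimental arm, telemedicine dates: "the respiratory therapist administers the study survey and conducts an rPFT from clinic with the patient in their home". The schedule repeats until the fifth clinic visit, "resulting in 5 in-person assessments and 8 intermediate tele-assessments over the course of approximately 12 months".
- Control arm: participants will "be required to complete a study survey each month". No administrator is named, and this arm has no telemedicine appointments.
- Both arms, general rule: "The initial survey administered at month 0 will be completed with a researcher present". Then: "The remaining surveys will be completed online". On order relative to testing: "If it coincides with administration of a PFT or rPFT, it will be administered first".

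The survey feeds a primary outcome. The Part 2 primary hypothesis (Section 1.1) has NIV thresholds met closer to the initiation criteria, "at a time when quality of life is higher, compared to the control group". Section 8.3 analyses as a primary outcome "whether QoL is better sustained at this point in individuals in the experimental group", using a Wilcoxon-Mann-Whitney test with no term for survey mode.

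**The concern.** The therapist sentence and the online sentence give different instructions for the same survey, and they stand in adjacent paragraphs. A site could follow either, or different staff could follow different ones.

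The stakes depend on which is followed. The SAQLI and MDRS-D are subjective self-reports. Answering questions put by a person may give different scores from answering an online form, and here that person conducts the extra monitoring and so knows the arm. If this happens in one arm only, the arm difference in quality of life mixes any effect of monitoring with any effect of survey mode. The planned two-sample test cannot separate them. The month 0 survey has a researcher present in both arms, so the imbalance would begin only after randomization.

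**Working it through.** **1. Survey and session counts.** Table 1 has surveys at months 0 to 12, which is 13, of which 12 are post-baseline. Clinic months are 0, 3, 6, 9 and 12, so telemedicine months are 1, 2, 4, 5, 7, 8, 10 and 11, which is 8. The plan's own totals agree:

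- Section 7.3, control: 13 × 15 min = 3.25 h. Experimental: 3.25 h + 8 × 30 min = 7.25 h.
- Section 14.0, control: 13 × $5 = $65. Experimental: $65 + 8 × $10 = $145.

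**2. Post-baseline survey mode under each reading of Section 7.2.2.**

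| Reading | Experimental arm | Control arm |
|---|---|---|
| Therapist sentence governs telemedicine dates | 8 by therapist, 4 online | 0 by therapist, 12 online |
| Online sentence governs everything after month 0 | 12 online | 12 online |

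The ordering rule says when the survey is given, not by whom or how, so it does not decide between the rows.

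**3. How much of the primary comparison would be affected.** I take quality of life at NIV recommendation to be the survey from the session at which the recommendation is made; the plan does not say so explicitly. Section 7.2.2 places recommendations at the end of a test session. Control-arm recommendations can therefore arise only at clinic visits, while experimental-arm ones can also arise in telemedicine months, which are 8/12 = 67% of follow-up months.

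For the FVC route (FVC at or below 50% predicted) this can be simulated from the Section 8.2 decline of 3.5 ± 3.4% per month. Section 8.2 gives no starting FVC, so every starting value below is an assumption.

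- *Rebuild of the Section 8.2 simulation.* Start at 82% predicted, independent normal monthly drops with mean 3.5 and SD 3.4. Threshold met: 81.5% with monthly and 80.5% with quarterly sampling (plan: 80.6%). Mean FVC at recommendation: 47.0% and 43.5% (plan: 47.0% and 43.4%). The plan's figures are closely reproduced. Share of experimental-arm first crossings in telemedicine months: 64%.
- *Constant slope per patient, normal with mean 3.5 and SD 3.4.* Uniform starting FVC of 51-80, 51-100, 60-100 and 70-110% predicted gives shares of 71%, 69%, 64% and 65%. These versions do not match the plan's 80.6% (74%, 65%, 61% and 52% meet the threshold) and serve only to test sensitivity.
- *Extreme case.* Independent drops with everyone starting at 100% gives 53%, but then only 25% meet the threshold, far from the plan's 80.6%.

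The share is thus roughly 60-70% under plausible starting values, against 0% in control. The second route to recommendation, dyspnea with MIP above -60 cm H2O, is not simulated because the plan gives no data for it.

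**4. Effect on the estimate.** Let *d* be the true arm difference, *m* the shift from live administration and *p* the affected share of experimental-arm values. The expected observed difference is *d* + *p* × *m*. Here *p* is about 0.6 to 0.7. The plan gives neither the size nor the sign of *m*.

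**The case against.** The strongest reply is that no arm difference exists. The paragraph devoted to the survey says it is completed online and allows no exception. It also uses the verb administer for the survey in both arms, so the therapist may only be prompting an online form. Table 1 marks the survey with one symbol in both arms, and Sections 7.3 and 14.0 time and pay for it separately from the rPFT. All this fits a common survey task. It does not settle the mode, and the therapist sentence still stands, so the contradiction survives; the arm difference is conditional on it.

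Three stronger readings are tempting, and the document does not support them.

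- *That mode does differ by arm.* This holds only if the therapist sentence governs. Nor does the text say that control surveys are self-completed: online completion leaves open who enters the answers and who is present.
- *That the bias favours the experimental arm.* Patients might report better quality of life to the person helping them, but live questions about breathlessness could also draw out more symptoms. The direction is unknown.
- *That the bias is a known fraction of the target.* A reader might assume a mode effect of 0.2 to 0.5 SD and, with the SAQLI SD of 1.6 and target of 1.52 in Section 8.2, obtain 0.637 × 0.2 × 1.6 = 0.20 to 0.637 × 0.5 × 1.6 = 0.51 points, or 13% to 34% of 1.52. The document has no source for 0.2 to 0.5, so the result only restates the assumption and does not show materiality.

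A remedy that kept the therapist from learning the survey answers would also go too far. Section 7.2.2 makes dyspnea part of one recommendation criterion and does not say how it is ascertained, so such a bar might remove information the therapist uses.

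**Conclusion.** Section 7.2.2 contradicts itself on survey mode, and nothing elsewhere resolves it. That much is certain from the text. If the therapist sentence is followed, 8 of 12 post-baseline surveys in the experimental arm and 0 of 12 in control are given by the person delivering the intervention. About 60-70% of experimental-arm quality-of-life values at FVC-based NIV recommendation would then come from such surveys, and no control values. The primary quality-of-life comparison would be confounded with survey mode, by an amount and in a direction that cannot be stated from the document.

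The 60-70% rests on assumed starting FVC, the decline rate in Section 8.2, the FVC route alone, and use of the same-session survey. If the online sentence governs, mode is the same in both arms and the point reduces to a drafting conflict. The correction is worth making because it is cheap and protects a subjective primary outcome in a trial of 20 per arm.

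**What to change.** In Section 7.2.2:

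- Delete the words that give survey administration to the therapist at telemedicine appointments.
- State that in both arms every survey after month 0 is completed online by the same procedure, before any PFT or rPFT held that day, with the same help with entry allowed in both arms, and that the therapist does not ask the questions.
- Record for each survey the mode actually used, and add to Section 8.3 a sensitivity check of the quality-of-life comparison by recorded mode.

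Do not add a rule that bars the therapist from dyspnea information relevant to the NIV recommendation criterion. It is enough that mode is stated and equal across arms.

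Cost: a few sentences and one extra data field, with no change to the visit schedule or payments. The downside is that a few more surveys may be missed in the experimental arm once they are no longer part of a live session.

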#### Part 2:

Patients:

- 1) Possess a diagnosis of definite, probable, probable laboratory-supported, or possible ALS by revised El Escorial research criteria.
- 2) Be 18 years of age or older.
- 3) Have a caregiver available to participate in the study.

- 4) Symptom onset within the last three years.
- 5) Intent to attend the Penn State Hershey ALS clinic every three months for the next year.
- 6) Have home wireless internet service sufficient for engaging in telemedicine sessions.

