## **7.0 Study Design and Procedures**

### **7.1 Study Design**

Part 1: This is a self-controlled study where each participant will be administered a standard of care PFT for measurement of FVC and MIP, as well as an rPFT, separated by at least an hour, for measurement of experimental FVC and MIP. The rPFT is guided by a respiratory therapist in another room, utilizing the telemedicine interface of the Hersey ALS clinic and devices for measuring FVC and MIP (**Error! Reference source not found.**).

Part 2: This is a randomized controlled study to determine whether regular monitoring of respiratory function at monthly, rather than every 3-month intervals, over the course of a year, can lead to better

**Figure 2: (A) Image of the telemedicine interface used by the Hershey ALS clinic. (B) The rPFT toolkit. From left to right: The GiO 4 respiratory pressure meter and mouthpiece, smartphone running the spirometry application, and Air Smart Spirometer and turbine.**

patient outcomes. In the experimental group, standard FVC and MIP measurements obtained by the respiratory therapist in the ALS clinic every 3 months are supplemented with telemedicine-guided rPFT performed at monthly intervals (**Error! Reference source not found. 1**). Controls receive standard PFT assessments only. Patient outcomes, NIV recommendation, quality of life, and survival over one year, will be compared between experimental and control groups.

The researcher and respiratory therapist will be present either in person or virtually for all study sessions and will guide the patient and caregiver in the appropriate use of the equipment. Two devices are used to measure two aspects of respiratory function:

1) Air Smart Spirometer, Pond Healthcare Innovation AB

The following information is paraphrased from the user manual, which is included in the “devices” page of the protocol.

“Air Smart Spirometer is intended to measure the forced expiratory volume in 1 sec (FEV1) and the forced vital capacity (FVC) in a forced expiratory maneuver. These measures can be used for the detection, assessment and monitoring of certain lung diseases. The Air Smart Spirometer is intended to be used by:

- Healthcare professionals trained to perform spirometry tests on patients.
- Adults trained by healthcare professionals or through self-learning who understand how to perform a high quality spirometry test.

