During each rPFT administration, the respiratory therapist will guide the patient and caregiver through three valid maneuvers of the FVC and MIP tests. The therapist informs the caregiver to prepare the spirometer by connecting it to the tablet and opening the associated application. The patient is told to sit as upright as possible for the measurement of FVC. They will be told that to do this they will 1) inhale maximally, 2) exhale as hard and fast as possible, and 3) continue to exhale until indicated by the therapist. The therapist will also demonstrate this procedure to the patient. The caregiver applies nose clips to block airflow through the nose, holds the turbine of the spirometer to the patient's mouth and performs three repetitions of this sequence, with periods of relaxation between testings. Testing is repeated further until the therapist is satisfied with three valid maneuvers. The application on the tablet computes the FVC and percentage predicted value using the NHANES III criteria [Hankinson1999]. The largest FVC from a valid run is recorded.

To perform the MIP test, the therapist instructs the patient to breathe normally. The caregiver turns on the GiO pressure meter and attaches the mouthpiece, which is placed in the mouth of the patient. The patient is told they will be asked to draw breath in as quickly and powerfully as possible, for at least one second. The therapist tells the caregiver to place a finger over the valve outlet so that no air flows through the mouthpiece during inhalation. Nose clips will be used. As the therapist instructs, the patient performs three repetitions of this task, noting the reading each time. The maximal negative pressure from a valid run is recorded.

Each piece of reusable equipment will be labeled with an identification number. A log of all loaned materials will be maintained by the researchers. This log, included in the supporting documents, will be maintained on REDCap. Before delivery of the system to the study participant, the each piece of equipment will be inspected and tested. This study will not collect prior medical therapy relevant to the use of the device. There are no restrictions on medicines or therapies used by the participants in this study.

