### **7.3 Duration of Participation**

Part 1: The study procedures, including screening, consent, assessment, and survey, are expected to take 45 minutes. Administration of the simulated PFT with patient participants will be performed on the day of a scheduled clinic visit.

Part 2: The participant team will be enrolled for approximately one year. During this time, participants will engage in approximately five standard PFT assessments as part of normal clinical activities, requiring no additional time commitment. All participants will complete monthly surveys which will take 15 minutes each. Those in the experimental arm will also complete eight rPFTs, each taking 30 minutes. Control participants will be required to devote approximately 3.25 hours over the course of the study, and those in the experimental arm will devote approximately 7.25 hours.

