## **11.0 Risks**

The risks posed to subjects in the study will be no different than those presented during standard of care administration of pulmonary function testing. At all times participants will complete the study procedures under the guidance of a licensed respiratory therapist. In addition to expert guidance, those participating in remote assessments will be required to have a caregiver present to aid the patient in case assistance is required.

Loss of confidentiality is a risk of this study, but steps are taken to protect the participants' identities. Personal information, clinical assessments, test results, and survey responses will be labeled with a participant code assigned by REDCap and stored in this database. All data containing PHI will be collected either from the electronic medical record or in person. Data transmitted through the Air Smart Spirometer app will be labeled with the user's subject code, gender, age, and height. No part of the telemedicine video or audio recordings will be permanently stored.

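### The Part 2 early-stop rule does not separate stopping home rPFT, scheduled in one arm only, from leaving the study, so it permits unequal missing data between arms

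*Combined protocol and SAP*

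**What the plan says.** Section 7.2.2 intends study procedures to run to month 12, whether or not non-invasive ventilation (NIV) has begun. It then adds that "The treating neurologist will make the decision to end the protocol early if the patient is unable to perform the procedures". It neither lists the procedures meant nor gives a criterion, and what ends is the protocol as a whole.

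The two arms have different procedures. Section 7.1 says "Controls receive standard PFT assessments only"; section 7.2.2 adds monthly surveys in both arms. For the experimental arm, 7.2.2 describes a schedule "resulting in 5 in-person assessments and 8 intermediate tele-assessments over the course of approximately 12 months", and 7.3 says "Those in the experimental arm will also complete eight rPFTs, each taking 30 minutes". Home testing leans on the caregiver: in 7.1, "The caregiver applies nose clips to block airflow through the nose, holds the turbine of the spirometer to the patient's mouth", and in section 11.0, "those participating in remote assessments will be required to have a caregiver present to aid the patient in case assistance is required".

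Section 3.3.1 lets the research team terminate if the participant team comes to meet an exclusion criterion. Section 3.3.2 gives withdrawn subjects an optional endpoint assessment, rules out further follow-up and permits replacement from the waitlist. Section 1.3 plans to record survival after study procedures are completed, but does not say whether that covers patients who stop early. Section 8.3 names a test for Part 2 but gives no analysis set and no handling of early stops.

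**The concern.** Take two comparable patients, one in each arm, who can attend clinic, perform the clinic test and answer surveys, but who cannot manage the home test. The experimental patient is unable to perform a scheduled procedure, and the rule permits the neurologist to end the protocol. The control was never scheduled for that procedure, so the rule is not triggered. If early ending is then treated as withdrawal under 3.3.2, the experimental patient's remaining surveys and clinic results are lost to the study, and someone else may take the place.

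A data loss that can depend on allocation weakens the randomised comparison. Part 2 randomises 20 per arm and expects 15 per arm to reach the NIV recommendation at which the primary outcomes are compared, so a few unequal losses matter. Replacement can restore the count, but not the patient who was randomised. The secondary hypothesis on maintained quality of life (QoL) is also exposed, because it depends on surveys throughout the year.

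**Working it through.** **1. Where the arms differ.** Breathing tests after month 0: experimental 8 rPFT + 4 clinic PFT = 12; control 4 clinic PFT. The ratio is 12:4, or 3:1, and eight of the twelve are of a kind that controls never face. The time budget in 7.3 agrees: 13 surveys x 0.25 h = 3.25 h for controls, and 3.25 + 8 x 0.5 = 7.25 h for the experimental arm.

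**2. Which patients the rule can treat differently.**

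| Inability | Experimental arm | Control arm |
|---|---|---|
| Cannot make the breathing manoeuvre at all | Fails rPFT and clinic PFT; seen monthly | Fails clinic PFT; seen quarterly |
| Cannot do the home test, can do the clinic test | Rule can be triggered | Rule not triggered |

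Only the second row is a difference in kind. The first is a difference in timing.

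**3. The plan's own figure.** Section 8.2: 20 x 0.75 = 15 evaluable per arm, 80% power, effect size 0.95 (0.95 x 1.6 = 1.52 SAQLI points). The plan states neither alpha nor sidedness; I assume alpha 0.05. With the t-test, noncentrality = 0.95 x sqrt(n1 n2/(n1 + n2)) and df = n1 + n2 - 2. At 15 and 15, noncentrality = 0.95 x sqrt(7.5) = 2.60, giving power of 81.4% one-sided and 70.9% two-sided. The n required for 80% is 14.4 (rounded up to 15) one-sided and 18.4 (19) two-sided. For the planned rank-sum test, dividing by 0.955 gives about 15.1 and 19.3. The stated figure therefore reproduces as a one-sided 0.05 calculation.

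**4. Power if k of the 15 experimental patients are lost before recommendation and controls stay at 15.** For example, at k = 5, noncentrality = 0.95 x sqrt(10 x 15/25) = 2.33 with 23 df.

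| k | Experimental n | One-sided | Two-sided |
|---|---|---|---|
| 0 | 15 | 81.4% | 70.9% |
| 1 | 14 | 80.1% | 69.3% |
| 2 | 13 | 78.7% | 67.5% |
| 3 | 12 | 77.1% | 65.5% |
| 4 | 11 | 75.2% | 63.2% |
| 5 | 10 | 73.0% | 60.6% |

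The documents give no stopping rate, so k is an assumption.

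**5. Is the FVC comparison biased?** The simulation in 8.2 is closely matched by independent monthly falls of 3.5 ± 3.4 points from an assumed baseline of 70-90% predicted: 47.0 against 43.4, effect 0.97 ± 0.35, 82.7% reaching the criterion (plan: 47.0, 43.4, 0.964 ± 0.343, 80.6%). I then used a wider assumed baseline of 60-100% and stopped experimental patients only, at a random month. Stopping was applied either to 10%, 20% or 30% of them, or to those falling more than 42 points in the year, with 20%, 40% or 60% of these stopped. Evaluable experimental patients fell from about 15.3 to between 14.1 and 11.6, a loss of about 1 to 4. Mean FVC at recommendation stayed at 47.0-47.1 against 43.4-43.6, and the effect at 0.92-0.96. For FVC the result is fewer patients, with little shift in the estimate.

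**The case against.** A reader might infer more than the documents support, in four ways.

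*That losing a caregiver or an internet connection triggers the rule in one arm only.* The sentence names the patient alone, so these routes are inferred from how rPFT is run. Section 3.1 requires a caregiver of every Part 2 patient, and "Have home wireless internet service sufficient for engaging in telemedicine sessions" is an entry criterion for both arms. Surveys after month 0 are online in both arms, and section 1.2 lists caregiver surveys for controls too. What remains is the patient who fails specifically at home testing.

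*That ending the protocol stops the clinic tests.* Section 7.3 treats them as ordinary clinical activity. The uncertainty is whether the study keeps using the results.

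*That the 12:4 count can be turned into stopping rates.* This needs a failure chance per session, which the documents do not give. It would also need that chance to be equal for home and clinic tests, sessions to be independent, and one failure to end participation. Section 7.2.2 instead describes a neurologist's judgement of inability.

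*That the bias must favour the experimental arm on QoL.* Inability from illness occurs in both arms, failure at home testing is not shown to track low QoL, and a patient stopped after recommendation has already contributed to the primary comparison.

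The rule is also discretionary: it permits unequal stopping and does not require it. All of this stands and narrows the point. It does not remove it, because no section separates stopping rPFT from leaving the study, and 3.3.2 closes off follow-up.

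**Conclusion.** The point holds as a cheap improvement. The plan permits an experimental patient who cannot continue home rPFT to be lost when a comparable control would be retained. The supportable consequence is unequal missing data. If 1 to 5 of the 15 expected evaluable experimental patients were lost before recommendation, one-sided power would fall from about 81% to 80-73% (two-sided, from about 71% to 69-61%).

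This rests on alpha 0.05, full retention of controls, no replacement, and early ending under 7.2.2 being handled as withdrawal under 3.3.2, which the plan does not say outright. QoL bias is possible, but its size and direction cannot be computed from the documents. For FVC, the illustrative simulation shows little bias.

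**What to change.** - **Section 7.2.2:** leave the judgement that a patient cannot do rPFT with the treating neurologist, and state that stopping rPFT does not end study participation. Unless consent is withdrawn, the scheduled monthly surveys, routine clinic PFT results and survival status continue to be collected to month 12 in both arms. Record which component stopped, the date and the reason.
- **Sections 3.3.1 and 3.3.2:** reconcile these with 7.2.2. Absence of follow-up and replacement conflict with collection to month 12. Termination on exclusion criteria also needs reconciling: the FVC/MIP criterion in 3.2 carries no time limit and overlaps with the event that Part 2 waits for, and monthly testing can find it sooner. Also state whether survival recording under 1.3 covers patients who stop early.
- **Section 8.3:** state that all randomised patients are analysed in their allocated arm, and how missing outcomes after an early stop are handled.

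The cost is a few sentences across these sections and a short reason field. No visits are added, because the surveys and clinic tests are already scheduled. A small downside is that experimental patients with fewer rPFTs slightly dilute the contrast in monitoring frequency.
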